5.1.2.1 Other imputations

For the date of initial diagnosis and the date of most recent relapse/progression, missing day is defaulted to the 15th of the month and missing month and day is defaulted to 01-Jan. When the imputed date is later than the date of informed consent, it will be re-imputed with the date of informed consent.

5.2 AEs coding/grading

Adverse events are coded using the Medical dictionary for regulatory activities (MedDRA) terminology.

AEs will be assessed according to the Common Terminology Criteria for Adverse Events (CTCAE) version 5.0.

CTCAE grading is by definition a 5-point scale generally corresponding to mild, moderate, severe, life threatening, and death. This grading system inherently places a value on the importance of an event, although there is not necessarily proportionality among grades (a grade 2 is not necessarily twice as bad as a grade 1).

5.3 Laboratory parameters derivations

Grade categorization of lab values will be assigned programmatically as per NCI Common Terminology Criteria for Adverse Events (CTCAE) version 5.0 (specify version used in the RAP). The calculation of CTCAE grades will be based on the observed laboratory values only, clinical assessments will not be taken into account. The criteria to assign CTCAE grades are given in Novartis internal criteria for CTCAE grading of laboratory parameters. The latest available version of the document based on the underlying CTCAE version 5.0 at the time of analysis will be used. For laboratory tests where grades are not defined by CTCAE v5.0, results will be graded by the low/normal/high (or other project-specific ranges, if more suitable) classifications based on laboratory normal ranges.

A severity grade of 0 will be assigned for all non-missing lab values not graded as 1 or higher. Grade 5 will not be used. For laboratory tests that are graded for both low and high values, summaries will be done separately and labelled by direction, e.g., sodium will be summarized as hyponatremia and hypernatremia.

Imputation Rules

CTC grading for blood differentials is based on absolute values. However, these data may not be reported as absolute counts but rather as percentage of WBC.

If laboratory values are provided as '<X' (i.e. below limit of detection) or '>X', prior to conversion of laboratory values to SI unit, these numeric values are set to X.

The following rules will be applied to derive the WBC differential counts when only percentages are available for a xxx differential.

$$\text{xxx count} = (\text{WBC count}) * (\text{xxx \%value} / 100)$$

Further derivation of laboratory parameters might be required for CTCAE grading. For instance, corrected calcium can be derived using the reported total calcium value and albumin at the same assessment using the following formula:

Corrected Calcium (mmol/L) = Calcium (mmol/L) + 0.02 [40 (g/L) - Albumin (g/L)]

For calculation of laboratory CTC grades 0 and 1, the normal range for derived corrected calcium is set to the same limits (in mg/dL) as for calcium.

CTC grades for the derived absolute WBC differential counts (neutrophils, lymphocytes) and corrected calcium will be assigned as described above for grading.

5.4 Statistical models

5.4.1 Analysis supporting primary objective(s)

Subject-level sensitivity, subject-level specificity and corresponded 95% CI will be calculated based on the binomial distribution (implemented using SAS procedure FREQ with EXACT statement for one-way tables) ([Clopper and Pearson 1934](#)).

5.4.2 Analysis supporting secondary objective(s)

For subject-level assessments and region-level assessments, their estimation and 95% CI will be calculated based on the binomial distribution (implemented using SAS procedure FREQ with EXACT statement for one-way tables) ([Clopper and Pearson 1934](#)).

For inter-reader variability, it will be assessed by Fleiss' Kappa (κ_1) statistic ([Fleiss 1971](#)) defined below:

$$\kappa_1 = \frac{\bar{P} - \bar{P}_e}{1 - \bar{P}_e}.$$

Let N represent the total number of participants who have evaluable $[^{68}\text{Ga}]$ Ga-DOTA-TATE PET/CT, n the number of central readings per participants received ($n = 3$), and k the number of outcome categories ($k = 2$). Participants are indexed by $i = 1, \dots, N$ and categories are indexed by $j = 1, \dots, k$. Let n_{ij} represent the number of readers who assigned the i th participant to the j th category. Then

$$P_i = \frac{1}{n(n-1)} \sum_{j=1}^k n_{ij} (n_{ij} - 1) \text{ and } \bar{P} = \frac{1}{N} \sum_{i=1}^N P_i ;$$
$$p_j = \frac{1}{Nn} \sum_{i=1}^N n_{ij} \text{ and } \bar{P}_e = \sum_{j=1}^k p_j^2.$$

A contingency table of N row by 2 (the number of outcome categories) will be obtained to summarize the frequency of agreements among the 3 readers for each case and each patient-level outcome (i.e. positive, negative). The counts across each of the N rows will sum up to 3 (number of readers).

Based on the contingency table as described above, a Fleiss's Kappa statistic and corresponding 95% confidence interval will be estimated based on asymptotic estimation of the standard error

$$(\text{i.e. } \widehat{se}(\kappa_1) = \frac{\sqrt{2}}{\sum_{j=1}^k p_j(1-p_j)\sqrt{Nn(n-1)}} \sqrt{\left(\sum_{j=1}^k p_j (1-p_j)\right)^2 - \sum_{j=1}^k p_j(1-p_j)(1-2p_j)})$$

([Fleiss, Nee, Landis 1979](#); [Fleiss J, Levin B, Paik MC 2003](#)) and the normality assumption (i.e. 95% CI can be calculated as: $\kappa_1 \pm 1.96\widehat{se}(\kappa_1)$).

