8.3.1 Imaging for tumor assessment

The imaging assessment collection plan for this study is presented in [Table 8-2](#).

Table 8-2 Imaging Assessment Collection Plan

Imaging procedure	Mandatory or Optional	Imaging Acquisition Timing
[¹¹¹ In]In-Pentetreotide SPECT/CT**	Mandatory - NENs patients only	screening*
High Resolution CT with contrasts (or MRI if CT with contrast is medically	Mandatory - NENs patients only	screening*

Imaging procedure	Mandatory or Optional	Imaging Acquisition Timing
contraindicated) of at least Chest, Abdomen and Pelvis (and any additional region as clinically indicated)		
[⁶⁸ Ga]Ga-DOTA-TATE PET/CT	Mandatory - all participants	Imaging day

*CIM assessment performed as a part of clinical practice within 2 months prior to imaging day, even before informed consent, can be used as long as imaging quality meets study defined criteria.

**If SPECT/CT is not available in the clinical site, SPECT can be acceptable.

[⁶⁸Ga]Ga-DOTA-TATE PET/CT imaging

[⁶⁸Ga]Ga-DOTA-TATE PET/CT imaging will be performed for all participants including HVs and PET/CT imaging will be submitted to the designated central CRO for independent central review. Three independent reviewers, who will be blinded to CIM and other patient data collected in clinical database will review PET/CT images. Central read results will not be provided to the treating physician/Clinical Study Investigator. If applicable for histopathology assessments detailed in Section 8.3.2, local read results of [⁶⁸Ga]Ga-DOTA-TATE PET/CT imaging will be used for the assessment.

CIM for NENs patient

CIM for patients with NENs must include [¹¹¹In]In-Pentetreotide SPECT/CT and High Resolution CT with intravenous and oral contrasts (or MRI if CT with contrast is medically contraindicated). A centralized reading of CIM for patients with NENs will be performed by a central independent reader who will be blinded to [⁶⁸Ga]Ga-DOTA-TATE PET/CT imaging results and other patient data collected in clinical database. Further details will be provided in the Imaging Manual.

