Region-level sensitivity, specificity, PPV, NPV, accuracy will be summarized respectively with corresponded exact 95% CI by regions. Region consists of liver, pancreas, gastrointestinal, lymph nodes and others.

Number of lesions detected by imaging

For region-level, number of lesion detected by [⁶⁸Ga]Ga-DOTA-TATE PET/CT imaging and CIM will be counted. Regarding [⁶⁸Ga]Ga-DOTA-TATE PET/CT imaging, individual and mean number of lesions detected by each 3 central readers will be presented. Regarding CIM, each number of lesions detected by [¹¹¹In]In-Pentetreotide SPECT/CT and High Resolution CT with contrast (or MRI if CT with contrast is medically contraindicated) will be presented.

Impact on treatment decision

Numbers and percentages of participants for each intended treatment plan collected from physician at pre and post [⁶⁸Ga]Ga-DOTA-TATE PET/CT imaging will be summarized. Summary statistics of participants for the change of intended treatment plan will also be presented.

Inter-reader variability

Inter-reader variability for [⁶⁸Ga]Ga-DOTA-TATE PET/CT imaging is defined as agreement rate among reader determinations and will be assessed by Fleiss' Kappa statistics. Inter-reader variability (%) and its normality 95% CI will be presented.

Lesion-level concordance rate for SSTR

The lesion-level concordance rate for SSTR between [⁶⁸Ga]Ga-DOTA-TATE PET/CT imaging local read and local histopathology result among lesions which is available, will be calculated. The rate is defined as the proportion of lesions which are positive or negative on both local read of [⁶⁸Ga]Ga-DOTA-TATE PET/CT imaging and local histopathology among lesions detected by local histopathology.

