1.1 Study design

This prospective, open-label, multi-center, single arm, phase III study, will enroll approximately 47 adult male or female participants with NENs and 23 HVs. Of all the participants with NENs, the number of participants with suspected NENs is limited to up to 5 with negative conventional imaging (CIM) result by central read in order to enroll sufficient number of participants with positive result in CIM. Negative CIM result by central read is applicable for patients who do not show any lesions based on CIM by central read. All eligible participants will undergo [⁶⁸Ga]Ga-DOTA-TATE PET/CT imaging. [⁶⁸Ga]Ga-DOTA-TATE will be administered intravenously at a single dose of 2 MBq/kg (0.054 mCi/kg) of body weight up to a maximum total dose of 200 MBq (5.4 mCi), and imaging will be acquired 40 to 90 minutes after the intravenous injection of [⁶⁸Ga]Ga-DOTA-TATE.

The purpose of this study is to evaluate the diagnostic performance of [⁶⁸Ga]Ga-DOTA-TATE PET/CT imaging compared with the CIM as standard of truth in patients with NENs and HVs. The data from this study will provide the evidence for diagnosis use of [⁶⁸Ga]Ga-DOTA-TATE PET/CT imaging in patient with NENs in Japan.

Figure 1-1 Study design

NENs: Neuroendocrine neoplasms, CT: Computed Tomography, MRI: Magnetic Resonance Imaging, CIM: Conventional Imaging, PET: Positron Emission Tomography

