2.1 Data analysis general information

The final analysis will be performed by Novartis. SAS version 9.4 or later and R version 4.3.1 or later will be used to perform all data analyses and to generate tables, figures and listings.

Data included in the analysis

Only one final analysis is planned for the co-primary endpoints. All statistical analyses will be performed using all data collected in the database up to the database lock date. The database lock date for the final analysis of study data will be established after all enrolled participants have completed End of study visit (Last Patient Last Visit).

All events with start date before or on the database lock date and not having documented end date will be reported as 'ongoing'. This approach applies, in particular, to adverse events, prior anti-neoplastic medication/ anti-neoplastic radiotherapies, and concomitant medication/ non-drug therapies/ non-drug procedures reports. For these cases, the end date will not be imputed and therefore will not appear in the listings.

For participants who have both High Resolution CT with contrast and MRI imaging as CIM, the results of MRI will be used for summaries. For participants who have multiple imaging assessments of the same modality on different imaging dates, the results on the latest assessment date will be used for summaries.

Participant categorization

For some efficacy analyses (subject/region-level sensitivity, specificity, PPV, NPV and accuracy), HVs will be categorized as CIM negative population (TN or FP) without CIM. If there are participants enrolled as patients with suspected NENs but founded not to have NENs based on CIM, they will be also categorized in this population.

Other than those above:

Analyses will be conducted by patients with confirmed/suspected NENs and HVs. Results will be presented by population unless otherwise specified.

General analysis conventions

Qualitative data (e.g., gender, race, etc.) will be summarized by frequencies and percentages; a missing category will be included as applicable. Percentages will be calculated using the number of participants in the relevant population or subgroup as the denominator.

Quantitative data (e.g., age, body weight, etc.) will be summarized by appropriate descriptive statistics (i.e. N, mean, standard deviation, median, 25th percentile, 75th percentile, minimum, and maximum).

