2.6.2 Statistical hypothesis, model, and method of analysis

Subject-level assessments

Subject-level PPV, NPV, accuracy will be summarized with corresponding exact 95% CI.

Region-level assessments

Region-level sensitivity, specificity, PPV, NPV, accuracy will be summarized respectively with corresponding exact 95% CI by regions.

Region consists of liver, pancreas, gastrointestinal, lymph nodes and others.

Number of lesions detected by imaging

Descriptive statistics for number of lesions will be provided by region-level and subject-level.

Regarding [⁶⁸Ga]Ga-DOTA-TATE PET/CT imaging, descriptive statistics of number of lesions for each of the 3 central reader , and 3 readers' mean number of lesions will be presented.

Regarding CIM, descriptive statistics of number of lesions detected by [¹¹¹In]In-Pentetreotide SPECT/CT and High Resolution CT with contrast (or MRI if CT with contrast is medically contraindicated) will be presented respectively.

Listing for number of lesions will be provided.

Impact on treatment decision

The number (%) of participants for intended treatment plan at pre and post [⁶⁸Ga]Ga-DOTA-TATE PET/CT imaging and the number (%) of participants for whom the intended treatment plan has changed and for whom it has not changed will be summarized. The number (%) of

participants will also be summarized for each combination of transition of intended treatment plan.

Listing for intended treatment plan will be provided.

Inter-reader variability

Each central read subject-level result (positive or negative), inter-reader variability (%) and its 95% CI will be presented.

Inter-reader variability will be assessed by Fleiss' Kappa (κ_1) statistic ([Fleiss 1971](#)). Refer to [Section 5.4.2](#) for details on Fleiss' Kappa.

An additional table will be presented to show the distribution of agreements with the number (%) of scans agreed by two readers and the number (%) of scans agreed by all three readers.

If one of the central readers is changed during the study and the total amount of its read is more than 30% of the total number of participants who have evaluable [⁶⁸Ga]Ga-DOTA-TATE PET/CT, inter-reader variability for each combination (before the change and after the change) and its normality 95% CI will be presented additionally. The distribution of agreements with the number (%) of scans agreed by two readers and the number (%) of scans agreed by all three readers will be also presented for each combination.

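### SAP 5.4.2 defines Fleiss' kappa over patients and healthy volunteers together, SAP 2.1 points to separate reporting, and the pooled value would say little about reader agreement in patients

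*SAP*

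**What the plan says.** SAP 5.4.2 gives the Fleiss' kappa formula for three central readings and two outcome categories. It opens with "Let N represent the total number of participants who have evaluable" PET/CT imaging and makes no split by population. HVs fall within that N: SAP 1.1 says the study "will enroll approximately 47 adult male or female participants with NENs and 23 HVs", and Protocol 8.3.1 says that "PET/CT imaging will be performed for all participants including HVs and PET/CT imaging will be submitted to" the central CRO, where three readers assess it.

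SAP 2.1 sets a different default. It begins "For some efficacy analyses (subject/region-level sensitivity, specificity, PPV, NPV and accuracy), HVs will be categorized as CIM negative population", so the listed diagnostic measures combine HVs with patients. All other analyses are done for patients and HVs separately, and "Results will be presented by population unless otherwise specified". Inter-reader variability is not among the listed measures, and neither SAP 2.6.2 nor 5.4.2 says in words that it is pooled.

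For the output, Protocol 9.4.1 states "Inter-reader variability (%) and its normality 95% CI will be presented" and SAP 2.6.2 states "Each central read subject-level result (positive or negative), inter-reader variability (%) and its 95% CI will be presented". Both documents call the endpoint an agreement rate assessed by kappa. SAP 2.6.2 also plans a table of scans on which two readers, or all three, agree. It states no split by population and no CI for that table.

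**The concern.** Kappa compares observed agreement with the agreement expected from the overall proportion of positive reads. If two groups with very different positive rates are pooled, agreement expected by chance falls to nearly one half, and telling a typical patient scan from a typical HV scan is enough to raise kappa. The pooled figure can then look substantial even when the readers agree no better than chance on which patients are positive. Both co-primary endpoints rest on central reads, and this endpoint tells a reader how far to trust them in the patients the product is meant for.

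The by-population reading has its own difficulty. In HVs nearly all reads should be negative, and there kappa is unstable or cannot be computed. The plan has no rule for that case.

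**Working it through.** **Inputs.** 47 patients and 23 HVs (SAP 1.1); n = 3 readings and k = 2 categories (SAP 5.4.2); planning sensitivity and specificity of 90% each (SAP 3). Assumed: each reader calls a patient positive with probability q and an HV positive with probability f, independently, so that kappa within each group is 0 in expectation. All 47 patients are treated as CIM positive.

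**The plan's own figures.** The documents state no expected kappa. The only figures given for the 47:23 mix are the power values in SAP Table 3-1, and they reproduce. At least 40 of 47 positive against 0.70 gives one-sided alpha 0.0138 and power 0.907 (stated 90.7%). At least 19 of 23 negative against 0.60 gives alpha 0.0190 and power 0.927 (stated 92.7%).

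**Pooled kappa.** In expectation:
- P̄ = {47[q² + (1−q)²] + 23[f² + (1−f)²]}/70
- p = (47q + 23f)/70, and Pe = p² + (1−p)²
- κ = (P̄ − Pe)/(1 − Pe)

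With q = 0.90 and f = 0.10: P̄ = 0.82; p = (42.3 + 2.3)/70 = 0.637; Pe = 0.538; κ = 0.282/0.462 = 0.61.

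With q = 0.90 and f = 0: P̄ = (38.54 + 23)/70 = 0.879; p = 42.3/70 = 0.604; Pe = 0.522; κ = 0.357/0.478 = 0.75.

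| Patient reads positive | HV reads positive | Pooled κ |
|---|---|---|
| 90% | 0% | 0.75 |
| 90% | 2% | 0.72 |
| 90% | 5% | 0.68 |
| 90% | 10% | 0.61 |
| 95% | 0% | 0.86 |
| 80% | 0% | 0.57 |
| 70% | 10% | 0.32 |

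Simulating 20,000 trials gave means of 0.748 (95% range 0.63 to 0.86) at 90%/0% and 0.610 (0.46 to 0.75) at 90%/10%. The patients-only kappa averaged −0.007.

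**Effect of the mix alone**, at 90%/0%: 47:0 gives 0, 60:10 gives 0.56, 47:23 gives 0.75 and 35:35 gives 0.82.

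**The planned CI.** With k = 2, the last sum in the SAP's standard error is p(1−p)[(1−2p) + (2p−1)] = 0, so the standard error reduces to √(2/(6N)) whatever the data. The half-width is 1.96 × √(2/420) = 0.135 at N = 70 and 1.96 × √(2/282) = 0.165 at N = 47. An interval of 0.61 ± 0.135 lies well above zero although agreement beyond chance within patients is nil.

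**HVs alone (23 scans, 69 reads).**
- All reads negative: P̄ = Pe = 1, so κ = 0/0.
- One stray positive read: P̄ = (22 + 1/3)/23 = 0.9710; Pe = 1 − 2(1/69)(68/69) = 0.9714; κ = −0.015 at 97% raw agreement.
- Two or three isolated positive reads: −0.030 or −0.045.
- Two readers positive on the same HV: +0.485. All three: 1.0.

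The chance that all 69 reads are negative is (1−f)^69: 50% at f = 1%, 25% at 2% and 0.1% at 10%.

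**A mixed example (assumed reads).** Patients: 42 with three positive reads, 2 with two, 1 with one, 2 with none. HVs: 22 with none, 1 with one. Pooled κ = 0.92; patients-only κ = 0.68, with raw pairwise agreement in patients of 45/47 = 96%.

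**The case against.** The strongest replies are these.

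- **Pooling is not certain.** Under the SAP 2.1 default, kappa and the agreement table would both be split, and patients would be seen on their own. This stands. A reader might infer that the plan will report a single pooled kappa and nothing else, but the documents support only an unreconciled pair of sections.
- **Pooling can be defended.** Blinded readers assess scans from both groups, and agreement over all of them matches the population behind the co-primaries taken together. Dependence on prevalence is a known property of kappa. This also stands, but it is a reason to state the choice and label the result.
- **Other outputs would show disagreement.** At 90% independent positive reads, all three readers agree on only 0.9³ + 0.1³ = 73% of patient scans, and the planned table would show about 80% even if pooled (HV rate 2%). SAP 2.5.6 also gives sensitivity and specificity for each reader. This softens the effect. However, the table has no stated split or CI, and the per-reader results appear only if both co-primaries are met and do not measure scan-by-scan agreement.
- **A patients-only kappa has the same weakness.** With 46 patients read positive by all three readers and one by two, κ = −0.007 at 98.6% raw agreement. This stands, and it rules out offering the patients-only kappa alone as the result.

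**Conclusion.** The point holds as a minor one. SAP 5.4.2 and 2.1 lead to different analyses and need reconciling. Under the literal pooled formula, readers with no agreement beyond chance within either group would score about 0.61 to 0.75 when 90% of patient reads are positive and 10% to 0% of HV reads are. Other patient rates widen this, for example to 0.57 at 80%/0% and 0.86 at 95%/0%. All of these rest on assumed read rates and independence within groups.

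Three stronger conclusions are tempting but unsupported. A single figure such as 0.72 needs a 2% HV read rate that appears nowhere in the documents; the SAP's planning rates give 0.61. The mix does not by itself set the value, because the read rates matter as well. The HV kappa is not always undefined or negative: it is positive when readers agree on the same HV, and at a 10% read rate it was zero or positive in 37% of simulated trials.

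The endpoint is secondary and descriptive, with no target kappa, so no trial decision turns on it.

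**What to change.** In SAP 2.6.2 and 5.4.2:

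1. State the population for kappa. Report it for patients with NENs beside the pooled value, and note that the pooled value depends on the designed patient/HV mix.
2. Split the planned agreement table by population. Add raw pairwise agreement (%) with a CI in patients and in HVs. With three readers and two categories, each scan contributes 1 if all agree and 1/3 otherwise. Pairwise agreement is therefore (1 + 2A)/3, where A is the proportion of scans with all three in agreement, and an exact CI for A converts directly.
3. Report no kappa in HVs. State that kappa is not estimable when all reads fall in one category, and that it must be read with raw agreement when positivity is near 0% or 100%. Both rules apply to the patients-only kappa too.
4. Label raw agreement as the rate (%) and kappa as a unitless statistic.

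Kappa by region in patients is optional. The cost is SAP wording and a few table rows, with no new data. The downside is that the patients-only kappa is less precise (half-width about 0.165 against 0.135 by the SAP's standard error) and is itself sensitive to high prevalence, so it should not stand alone.

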2.2 Analysis sets

Full Analysis Set

The Full Analysis Set (FAS) comprises all enrolled participants.

Enrollment will take place at the time when all eligibility requirements are confirmed.

Efficacy Analysis Set

The Efficacy Analysis Set (EFF) comprises all enrolled participants who were administered with [⁶⁸Ga]Ga-DOTA-TATE. Patients with confirmed/suspected NENs must have both results of [⁶⁸Ga]Ga-DOTA-TATE PET/CT imaging and CIM. HVs must have result of [⁶⁸Ga]Ga-DOTA-TATE PET/CT imaging. If at least 1 central reader cannot judge results for all CIM or

[⁶⁸Ga]Ga-DOTA-TATE PET/CT imaging due to imaging quality, the results are considered as "Not evaluable". Those participants will be excluded from the EFF.

A result considered "Not evaluable" if the following scenarios happened:

- There is no subject-level result due to poor imaging quality or insufficient coverage.
- There is no accurate subject-level result because one or more region-level result are not readable and all other region-level result are negative.

Safety Set

The Safety Set comprises all participants who received any dose of [⁶⁸Ga]Ga-DOTA-TATE.

Pharmacokinetic Analysis Set

The Pharmacokinetic Analysis Set (PAS) includes all participants who provided at least one evaluable PK concentration. A profile is considered evaluable if all of the following conditions are satisfied:

- Participant received the study drug
- Participant provided at least one primary PK parameter

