2.6 Analysis supporting secondary objectives

All analyses supporting secondary objectives will be performed for the EFF.

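### Inter-reader agreement is computed only on PET/CT scans that all three readers could judge, so disagreement about readability is left out and the reported agreement is likely, though not certainly, overstated

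*SAP*

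**What the plan says.** The restriction comes from four SAP sections read together.

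- **SAP 2.2 (also Protocol 9.1).** The rule opens "If at least 1 central reader cannot judge results for all CIM or" the PET/CT because of image quality; the result is then not evaluable. The consequence is "Those participants will be excluded from the EFF". SAP 2.2 adds a second route: "There is no accurate subject-level result because one or more region-level result are not readable and all other region-level result are negative".
- **SAP 2.6.** "All analyses supporting secondary objectives will be performed for the EFF".
- **SAP 2.6.2.** Inter-reader variability is assessed by Fleiss' kappa, with a further table of scans agreed by two readers and by all three. Neither has a readability category.
- **SAP 5.4.2.** N is set by "Let N represent the total number of participants who have evaluable" PET/CT, and n is "n the number of central readings per participants received", fixed at 3. The table has one column for "each patient-level outcome (i.e. positive, negative"), so k = 2. "The counts across each of the N rows will sum up to 3 (number of readers").

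SAP 2.6.6 plans no supplementary analyses for secondary endpoints. The reanalysis in SAP 2.5.6 that counts excluded participants as all positive or all negative covers the primary endpoints only, and runs only if these are met. SAP 2.5.2 lists the central imaging assessments for the FAS.

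**The concern.** SAP 2.6.1 defines the endpoint as agreement among reader determinations. If two readers give a result and the third cannot, the readers have differed, yet the row would not sum to 3 and the scan is removed. The scans are thus selected on the readers' own output, which is what the endpoint is meant to measure.

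The second route in SAP 2.2 shows that more than image quality can be lost. Suppose one reader sees a liver lesion, while another calls every readable region negative and one region unreadable. The second reader's result is not evaluable, so the scan is dropped, although these two readers differ on whether a lesion was seen. Had the second reader called any region positive, that read would have stayed evaluable despite the unreadable region.

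The reported N need not reveal this. SAP 3 continues enrolment until 70 participants are in the EFF, so agreement could be reported on 70 scans however many were removed. At stake is how the reproducibility figure is read.

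**Working it through.** **Plan's own figures.** The documents state no expected kappa, agreement rate or not-evaluable rate. The one planning figure used here is the EFF of 70. Its powers in SAP Table 3-1 reproduce with the exact binomial test: N = 47 needs 40 positives, power 90.7%; N = 23 needs 19 negatives, power 92.7%.

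**Formula (SAP 5.4.2).** P_i = Σ n_ij(n_ij − 1) / [n(n − 1)] with n = 3. P̄ is the mean of P_i, P̄_e = Σ p_j², and κ = (P̄ − P̄_e)/(1 − P̄_e).

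**Step 1: contribution of each kind of scan to P̄.**

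- Retained, unanimous (3,0): 6/6 = 1.
- Retained, split (2,1): 2/6 = 1/3.
- Dropped, readers split on readability, counted with a third category: (2,0,1) or (1,0,2) gives 1/3; (1,1,1) gives 0.
- Dropped, unreadable to all three (0,0,3): 1.

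The mean over retained scans is at least 1/3, so dropping split-readability scans can never lower raw agreement. They are never unanimous, so dropping them can never lower the unanimity rate either. Dropping scans unreadable to all three can never raise raw agreement or unanimity.

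**Step 2: illustration with assumed counts.** Take 70 evaluable scans: 42 +++, 24 −−−, 2 ++−, 2 +−−.

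- ΣP_i = 66 + 4/3 = 67.333, so P̄ = 67.333/70 = 0.9619.
- Reads are 132 positive and 78 negative of 210, so P̄_e = 0.6286² + 0.3714² = 0.5331.
- κ = (0.9619 − 0.5331)/(1 − 0.5331) = 0.918. Unanimous: 66/70 = 94.3%.

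Dropped scans are now put back with not evaluable as a third category (k = 3). Each split-readability scan has one reader unable to judge.

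| Scans put back | P̄ | P̄_e | κ | Unanimous |
|---|---|---|---|---|
| 3 split, other two both positive | 0.9361 | 0.5241 | 0.866 | 66/73 = 90.4% |
| 3 split, other two both negative | 0.9361 | 0.5106 | 0.869 | 90.4% |
| 3 split, other two disagree | 0.9224 | 0.5170 | 0.839 | 90.4% |
| 5 split, other two both positive | 0.9200 | 0.5190 | 0.834 | 66/75 = 88.0% |
| 5 split, other two both negative | 0.9200 | 0.4976 | 0.841 | 88.0% |
| 5 split, other two disagree | 0.8978 | 0.5073 | 0.793 | 88.0% |
| 3 unreadable to all three | 0.9635 | 0.4918 | 0.928 | 69/73 = 94.5% |

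**Step 3: is the direction for kappa fixed?** No, because P̄_e moves as well. Over 4,770 assumed configurations of 70 retained scans with 1, 3 or 7 split-readability scans put back, kappa rose in 1,208. All of these started at a kappa of 0.57 or less; above that, kappa always fell.

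The mix matters too. Take 43 +++, 20 −−−, 4 ++− and 3 +−−, with kappa 0.850. Putting back 1 split scan (two negative reads, one unreadable) and 3 scans unreadable to all gives 0.854, slightly higher.

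**The case against.** The strongest reply is that the SAP chose its target openly: positive/negative agreement on evaluable scans. Readability is a technical judgement, and a third nominal category answers a different question. This stands in part. If that is the target, the restriction belongs to the definition and is not an error. The result should then be labelled as conditional, and the SAP does not do this.

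A reader might infer that agreement is necessarily biased upward, or that the exclusion can only raise it. The documents do not support that. The same rule drops scans unreadable to all three readers, which count as agreement once readability is an outcome. Kappa can move either way when it starts low. The mix of unreadable scans is not given, and the counts of 3 and 5 above are invented for illustration.

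The effect is also modest beside the planned interval. With k = 2 the last sum in the printed standard error is zero, so it reduces to √(1/(3N)) = √(1/210) = 0.069 at N = 70, a half-width of 1.96 × 0.069 = 0.135. The largest drop in the table is 0.918 − 0.793 = 0.125. Imprecision does not excuse an undisclosed selection, but it limits its weight.

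Some transparency exists already: the FAS listing of central reads, and the analysis-set counts in SAP 2.3.1. These let a reader find the dropped scans but give no agreement statistic that includes them.

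Finally, the endpoint is descriptive, with no threshold or success rule. That stands.

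**Conclusion.** The point holds as a reporting gap in a secondary endpoint. Planned agreement is conditional on all three readers judging the scan. As a measure of agreement among reader determinations it is likely overstated if split-readability scans occur and agreement is moderate to high. In the illustration the drop is about 0.05 to 0.08 in kappa for 3 such scans and 0.08 to 0.13 for 5; the 3 unanimously unreadable scans move it up by 0.01.

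These sizes rest on assumed counts and on treating not evaluable as a third outcome. If every scan is judged by all three readers, the gap has no effect. A reader might also infer that the sensitivity and specificity results are called into question here; this point concerns only the agreement endpoint. The change is worth making because it is cheap, but nothing in the trial's success criteria depends on it.

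**What to change.** Keep the two-category kappa and agreement table, and label both as conditional on all three readers judging the scan. Beside them report:

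- Fleiss' kappa and the agreement table with k = 3 (positive, negative, not evaluable), for all participants with a PET/CT submitted for central read;
- separate counts of scans on which readers split on readability and of scans unreadable to all three.

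The point-estimate formula in SAP 5.4.2 is already written for general k. Naming this population would also avoid a small ambiguity: SAP 2.6 uses the EFF, which drops patients whose CIM is not evaluable, while SAP 5.4.2 refers only to evaluable PET/CT.

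The cost is one extra table and an agreement figure that may be slightly less favourable. The central reads are already to be listed for the FAS, so no new data should be needed.
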